3.1 Preparation, organization and management of phase 1 study

The primary objective of this exploratory phase 1 study is to evaluate which ophthalmological measures optimally differentiate between A β -positive, clinically probable AD patients and A β -negative, cognitive-intact healthy controls, matched for age, education, gender and apoE status.

Methodology

Study cohorts:

1. Fifteen clinically probable AD patients, according to the National Institute of Aging (NIA)-Alzheimer's Association (AA) diagnostic criteria,⁵ with an MMSE of 12 or higher, and with a positive CSF biomarker analysis or a positive amyloid-PET scan in the past or a positive amyloid-PET scan at inclusion, will be included in this group. Patients will be recruited via the memory clinic UZ

Leuven, which is headed by Prof. dr. [name] (total number of dementia patients due to AD currently in follow-up = 486).

2. Fifteen A β -negative cognitive-intact healthy controls will be recruited from a longitudinal cohort of 180 cognitively healthy older adults who are followed at the Laboratory for Cognitive Neurology of Prof. dr. [name] (UZ Leuven) (mean age = 68.4 \pm 6.4, range 55-80 years).^{6,7} These community-dwelling participants were first recruited between 2010 and 2015 for multimodal brain imaging (A β PET and volumetric MRI) combined with neuropsychological assessment. One of the key inclusion criteria was neuropsychological test scores within the published norms at baseline. This cohort has been well characterized at baseline by means of detailed evaluation of lifestyle factors (lifelong cognitive and physical activity), quantitative parameters (weight, height, blood pressure under standardized conditions), cognitive reserve score (Cognitive Reserve Questionnaire), and neuropsychological performance. Participants are longitudinally followed with neuropsychological assessments at two-yearly intervals. The ready availability of this deeply phenotyped cohort is a strength of this project.

A β -negative cognitive-intact controls will be matched to the AD patients for age, gender, education and apoE status. The A β -negative status and the cognitive-intact status will be verified by a repeat A β PET scan and a neuropsychological assessment at inclusion in the current study.

Study procedures:

After signing the informed consent, patients will be asked to fill in a questionnaire. All eligible participants will then undergo detailed ophthalmological examination, an MRI scan, ¹⁸F-flutemetamol PET scan, blood sampling (apoE genotyping and fasting laboratory tests – Table 1), as well as a detailed neuropsychological assessment.

Hematology	Chemistry	Genotyping
Hematocrit	Gamma GT	apoE polymorphism
Hemoglobin	Alkaline phosphatase	
Platelet count	Alanine aminotransferase (ALT)	
WBC (total and differential)	Aspartate aminotransferase (AST)	

Sedimentation rate	Bicarbonate	
	Calcium	
	Chloride	
	Potassium	
	Sodium	
	Creatinin	
	Urea	
	Low-density Lipoprotein	
	C-reactive protein	
	Glycemia	
	HbA1c	

Table 1: Laboratory tests

- Ophthalmological examination will include visual acuity measurement, biomicroscopy and funduscopy, followed by the acquisition of hyperspectral, (angio-) OCT, and fundus photography using predetermined protocols.
- PET images will be acquired on a TruePoint Siemens PET scanner using static acquisition during an acquisition window of 30 minutes, starting 90 minutes post-injection. A low-dose computed tomography scan will be performed for attenuation correction, prior to the PET scan. The summed ¹⁸F-flutemetamol PET image (sumPET) will be co-registered to the subjects' T1-weighted MRI image. Segmentation parameters from the subjects T1-weighted MRI will be used to normalize the co-registered sumPET. A Standardized Uptake Value Ratio (SUVR) image will be created by dividing the normalized sumPET image by the uptake in the cerebellar grey matter reference region. SUVR values will then be calculated in a composite volume of interest (VOI) (SUVRcomp), consisting of frontal, parietal, anterior cingulate, posterior cingulate and lateral temporal VOIs, masked by the subject-specific gray matter map.⁶
- MRI will be performed on a 3T Achieva dstream Philips MRI scanner with a 32-channel head coil. The MRI sequence will consist of an MPRAGE volumetric MRI, and a FLAIR and Gradient Echo sequence.

- The Neuropsychological test battery will consist of the Auditory Verbal Learning Test (AVLT), Repeatable Battery for the Assessment of Neuropsychological Status (RBANS), Raven's Progressive Matrices (RPM), Mini Mental State Examination (MMSE), Neuropsychiatric Inventory (NPI), and Cornell Scale for Depression in Dementia (CSDD).

Statistical analysis:

The primary statistical analysis will be based on a Receiver Operating Characteristic analysis of the different ophthalmological measures, to determine which have the best diagnostic accuracy (area under the curve) compared to the binary A β PET classification as standard-of-truth. In the cross-sectional studies, the standard-of-truth will consist of the binary distinction between A β -positive cases and A β -negative cases, based on A β PET. This distinction will rely on a semi-quantitative analysis and a cut-off based on independent data.⁷ The phase 1 study is considered exploratory and the diagnostic accuracy of a wide range of ophthalmological parameters will be assessed. The three ophthalmological parameters with the best diagnostic accuracy will be selected as primary outcome measures for further validation in the phase 2 study in an independent cohort.

3.2 Preparation, organization and management of phase 2 study

The primary objective of this study is to evaluate the diagnostic accuracy of three ophthalmological measures, selected based on the phase 1 study, for discriminating between A β -negative and A β -positive healthy cognitive-intact older adults and for discriminating between A β -negative cognitive-intact older adults and A β -positive MCI patients.

Methodology

Study cohorts:

1. Patients with amnestic MCI due to AD (A β -positive MCI), according to the NIA-AA diagnostic criteria, an MMSE 24 or higher, and with a positive CSF biomarker analysis or a positive amyloid-PET scan in the past or a positive amyloid-PET scan at inclusion, recruited via the memory clinic UZ Leuven (total number of amnestic MCI patients currently in follow-up = 64).
2. A β -positive cognitive-intact older adults. These will be recruited from the longitudinal cohort of older adults followed at the Laboratory for Cognitive Neurology described above. At inclusion

(between 2010-2015) 30 out of 180 participants were A β -positive. A positive CSF biomarker analysis or a positive amyloid-PET scan in the past or a positive amyloid-PET scan at inclusion is a prerequisite for inclusion in this group.

3. A β -negative cognitive-intact older adults, recruited from the same longitudinal cohort.

Study procedures:

cfr. Phase 1 study

Statistical analysis:

The primary analysis will be based on a contingency table, in which cognitively intact subjects will be classified according to one ophthalmological parameter and compared to the classification based on the A β PET. This will be done for the three parameters that have been selected based on the phase 1 data. The same will be done for the classification of the cognitively intact A β -negative cases versus the A β -positive MCI cases.

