8.1 Sample size

Phase 1: based on previous trials on OCT measurements in AD and age-matched cognitive-intact controls,⁹ a sample size of 8 patients would be sufficient to discriminate both groups using a two-tailed t-test with alpha 0.05, a power of 0.90 and an estimated effect size of 2.73 µm (RFNL change). For this proof-of-concept study, we aim to recruit 15 patients per group.

Phase 2: based a previous trial,¹⁰ comparing OCT measurements in Aβ-positive versus Aβ-negative cognitive-intact subjects, the target sample size is at least 13 patients per group (alpha = 0.05, power = 0.90, estimated effect size of 1.33). We aim to include 20 patients in each group.

Longitudinal: all participants of the phase 1 and phase 2 study (n = 90) will be invited to participate in the longitudinal component.

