8.2 Analysis

Cfr. Paragraph 3.

9. Quality assurance

To assure maximal quality and reproducibility, the trial protocol will be followed rigorously.

10. Direct access to source data and documents

Only data gathered in the context of the trial will be used.

11. Ethics and regulatory approvals

The trial will be conducted in compliance with the principles of the Declaration of Helsinki (2008), the principles of Good Clinical Practice and in accordance with all applicable regulatory

requirements. This protocol and related documents will be submitted for review to Ethics Committee of the University Hospitals Leuven.

The Study will be conducted only on the basis of prior informed consent by the Subjects to participate in the Study. We shall obtain a signed informed consent form (ICF) for all patients prior to their enrollment and participation in the Study in compliance with all applicable laws, regulations and the approval of the (local) Ethics Committee, if required. We shall retain such ICFs in accordance with the requirements of all applicable regulatory agencies and laws.

12. Data Handling

We shall treat all information and data as confidential and shall not disclose such information to any third parties or use such information for any purpose other than the performance of the Study. The collection, processing and disclosure of personal data, will comply with applicable personal data protection and the processing of personal data (Directive 95/46/EC and Belgian law of December 8, 1992 on the Protection of the Privacy in relation to the Processing of Personal Data). We will protect the data from disclosure outside the research according to the terms of the research protocol and the informed consent document. The subject's name or other identifiers will be stored separately from their research data and replaced with a unique code to create a new identity for the subject.

13. Data Management

All data will be analyzed and stored in a coded fashion, with a unique anonymous identifier for every subject. In the future, these data could be used in the context of this project, and for related projects regarding cognitive functions, Alzheimer's disease and related conditions.

14. Translational research

From every included patient, a blood sample will be collected and stored for genotyping and biochemical analysis.

15. Publication Policy

Any publication will be submitted to all co-authors at least thirty (30) days prior to submission or disclosure.

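### The phase 2 sample size (13 per group, power 0.90) is worked out for a comparison of two means, but the primary analysis is a set of contingency tables, and the MCI contrast has no stated effect

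*Protocol*

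**What the plan says.** The primary objective in section 3.2 is to "evaluate the diagnostic accuracy of three ophthalmological measures, selected based on the phase 1 study", in two contrasts: amyloid-negative against amyloid-positive cognitively intact adults, and amyloid-negative intact adults against amyloid-positive MCI patients.

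The analysis paragraph of section 3.2 reads: "The primary analysis will be based on a contingency table, in which cognitively intact subjects will be classified according to one ophthalmological parameter", with amyloid PET as the comparator. It adds "This will be done for the three parameters that have been selected based on the phase 1 data", and for the second contrast "The same will be done for the classification of the cognitively intact" amyloid-negative cases against the amyloid-positive MCI cases. This makes 3 × 2 = 6 tables.

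Section 8.1 takes the phase 2 size from an earlier OCT study in "cognitive-intact subjects, the target sample size is at least 13 patients per group (alpha = 0.05, power = 0.90, estimated effect size of 1.33"), and then says "We aim to include 20 patients in each group". No test is named for phase 2. The only test named in section 8.1 belongs to phase 1, where the number "would be sufficient to discriminate both groups using a two-tailed t-test with alpha 0.05". Section 8.2 adds no further analysis; it says only "Cfr. Paragraph 3".

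**The concern.** The 0.90 in section 8.1 appears to belong to a comparison of means on a continuous OCT measure. Section 3.2 plans no such comparison for phase 2, and section 8.2 adds none. Cutting a continuous measure in two loses information, so power worked out for means does not carry over to a table.

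Phase 2 is the independent validation of the three parameters chosen in phase 1. A reader of section 8.1 would take 20 per group to be comfortably above a minimum of 13 that already gives 0.90, and would assume that this covers both primary contrasts. The effect of 1.33 comes from intact subjects only, so section 8.1 offers nothing by which to judge the MCI contrast.

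**Working it through.** **Inputs from the protocol.** Section 8.1: alpha 0.05, power 0.90, effect size 1.33, minimum 13 per group, planned 20 per group. Section 3.2: 2×2 tables, three parameters, two contrasts.

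**Assumptions not in the protocol.** The effect of 1.33 is a standardised mean difference d. The test is two-sided. The measure is normal with equal variances. The cut-off is at the midpoint, which is the best point under that model. One table is tested at 0.05 without adjustment.

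**Step 1: reproduce the 13.** For a two-sided two-sample t-test, df = 2n − 2, the noncentrality is δ = d√(n/2), and power = P(|T(df, δ)| > t(0.975, df)).

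| n per group | df | δ | critical t | power |
|---|---|---|---|---|
| 12 | 22 | 1.33 × √6 = 3.258 | 2.074 | 0.875 |
| 13 | 24 | 1.33 × √6.5 = 3.391 | 2.064 | 0.902 |
| 20 | 38 | 1.33 × √10 = 4.206 | 2.024 | 0.984 |

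Solving for power 0.90 gives n = 12.92, hence 13. The plan's figure is correct arithmetic for a t-test. The normal approximation gives 12, and the one-sided versions give 10 (normal) and 11 (t).

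**Step 2: the same separation as a table.** Sensitivity = specificity = Φ(d/2) = Φ(0.665) = 0.747. The proportions classified positive are p₁ = 0.747 in the amyloid-positive group and p₂ = 0.253 in the amyloid-negative group, with mean 0.5.

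Normal approximation with pooled null variance: power = Φ{[(p₁ − p₂)√n − 1.96√(2 × 0.5 × 0.5)] / √(p₁(1 − p₁) + p₂(1 − p₂))}. The denominator is √(2 × 0.747 × 0.253) = 0.615.

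- n = 13: (0.494 × 3.606 − 1.386)/0.615 = 0.64, so power is 0.74.
- n = 20: (0.494 × 4.472 − 1.386)/0.615 = 1.34, so power is 0.91.

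For Fisher's test and the uncorrected chi-square test, power is the sum of binomial probabilities over all tables with p ≤ 0.05. Actual size is evaluated at p₁ = p₂ = 0.5.

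| n per group | Fisher | chi-square | normal approx. | t-test on means | actual size, Fisher / chi-square |
|---|---|---|---|---|---|
| 13 | 0.67 | 0.81 | 0.74 | 0.90 | 0.029 / 0.076 |
| 20 | 0.82 | 0.89 | 0.91 | 0.98 | 0.020 / 0.043 |

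At 13 the chi-square figure is flattered, because its actual size is above 0.05.

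**Step 3: effect with power 0.90 at 20 per group.** For the mean comparison d = 1.05. For one table d = 1.31 (normal approximation), 1.35 (chi-square) or 1.48 (Fisher).

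**Step 4: the MCI contrast.** No effect is stated, so a range is assumed, with 20 per group and one table:

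| assumed d | Fisher | chi-square | normal approx. |
|---|---|---|---|
| 1.0 | 0.55 | 0.67 | 0.69 |
| 1.5 | 0.91 | 0.95 | 0.96 |

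**Step 5: if the tables are descriptive.** The exact (Clopper-Pearson) 95% interval for 15/20 is 0.51 to 0.91. The expected width at a true value of 0.747 is 0.39 with 20 subjects and 0.48 with 13.

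**The case against.** The trial plans 20 per group, not 13, and at 20 two of the three table calculations (0.89 and 0.91) sit at the stated 0.90. Fisher's 0.82 partly reflects its conservatism, since its actual size there is 0.020. Section 8.1 claims no power for 20 per group, and it does say that the effect comes from OCT measurements in intact subjects. Section 3.2 names no hypothesis test and the synopsis speaks of sensitivity and specificity, so the tables may well be descriptive and every table-power figure hypothetical. The t-test for phase 2 is itself inferred. Using one contrast to size a second is ordinary practice, and no deficit is shown for MCI.

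Much of this stands. The mismatch does not show the intact contrast to be underpowered at 20, the sizes depend on the assumed model, and the MCI point is a gap rather than a wrong number. What does not fall is the main point: the protocol states a power and a primary analysis, and the first is not a property of the second. The descriptive reading does not rescue section 8.1 either, because a power for means is no justification for estimating sensitivity and specificity from 20 subjects each. An analysis plan could add the cut-off and the interval method, but the protocol's own sample-size rationale would still refer to a different analysis.

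**Conclusion.** The concern holds and should be fixed. The 13 per group at power 0.90 is correctly computed for a single two-sided comparison of means in cognitively intact subjects, but it does not describe the tables that section 3.2 makes primary. Under the normal, equal-variance, best-cut-off model with d = 1.33, one unadjusted table falls clearly short of 0.90 at 13 per group. At the planned 20 the difference from 0.90 is modest and depends on the test, and what is lost is the reserve that the mean comparison would show. The MCI contrast cannot be assessed from the protocol. The mismatch itself is certain, apart from the inference that phase 2 used a t-test, which rests on the exact match at 13 and the wording for phase 1. The size of its effect depends on the model, because the protocol gives no cut-off, standard deviation or expected sensitivity and specificity.

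**What to change.** Reword section 8.1 in three places.

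1. State, at 20 per group, the power of the section 3.2 tables with the test and the assumed sensitivity and specificity. If the tables are descriptive, state instead the expected confidence-interval width for sensitivity and specificity.
2. Label the figure of 13 per group at 0.90 as applying only to one comparison of means in cognitively intact subjects.
3. Give the effect assumed for the MCI contrast, or say that this contrast is not formally powered.

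The sample size and the primary analysis can stay as they are. The cost is a few sentences, with no extra patients, visits or analyses. The only drawback is that the stated figure becomes less favourable.

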18 DEC 2017

Date

Name: [name]. [name]

Co-Investigator

23-11-2017

Date

Name: [name]. [name]

Table of Contents

Table of Contents	3
1. Study Synopsis.....	5
2. Background, rationale and novelty	7
3. Trial objectives and design	8
3.1 Preparation, organization and management of phase 1 study.....	9
3.2 Preparation, organization and management of phase 2 study.....	12
3.3 Preparation, organization and management of longitudinal follow-up	13
4. Selection and withdrawal of subjects	15
4.1 Inclusion criteria	15
4.2 Exclusion criteria	15
4.3 Expected duration of trial.....	16
5. Trial procedures.....	16
5.1 MRI and ¹⁸ F-flutemetamol PET-CT scans.....	16
5.2 Sample collection and handling	16
5.3 Genetic analysis.....	16
5.4 Fasting laboratory test analysis.....	16
5.5 Ocular exams	16
5.6 Summary of visits/procedures	17
5.7 Supervision and responsibilities	17
5.7.1 Insurance	18
5.7.2 Informed consent	18
6. Assessment of efficacy	18
7. Assessment of safety.....	18
8. Statistics	19
8.1 Sample size	19

8.2 Analysis.....	19
9. Quality assurance	19
10. Direct access to source data and documents.....	19
11. Ethics and regulatory approvals.....	19
12. Data Handling	20
13. Data Management.....	20
14. Translational research.....	20
15. Publication Policy	21
16. Financial Aspects	21
17. References.....	22

1. Study Synopsis

Title of clinical trial	Multimodal retinal imaging in the detection and follow-up of Alzheimer's disease
Protocol Short Title/Acronym	RetAD
Sponsor name	UZLeuven
Principal Investigator	[name]. [name]
Medical condition or disease under investigation	Alzheimer's disease
Purpose of clinical trial	To evaluate the use of non-invasive, multimodal retinal imaging for the early detection of Alzheimer's disease and for the evaluation of disease progression
Primary objective	To identify retinal biomarkers for Alzheimer's disease by means of non-invasive, multimodal retinal imaging
Secondary objective(s)	
- To evaluate the diagnostic performance of selected ocular biomarkers for Alzheimer's disease- To deliver a proof-of-concept for the use of retinal biomarkers to quantitatively measure cerebral Aβ load

	
- To deliver a proof-of-concept for the use of retinal biomarkers to follow Alzheimer's disease progression
Trial Design	Observational, cross-sectional and prospective cohort

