Endpoints	
- Technical capability to detect Alzheimer's disease by means of non-invasive retinal imaging- Technical capability to follow up Alzheimer's disease progression by means of non-invasive retinal imaging
- If acceptable technical capability demonstrated: determination of diagnostic accuracy of multimodal retinal imaging in Alzheimer's disease (sensitivity and specificity)
Sample Size	90 individuals (35 amyloid-negative, 55 amyloid-positive)
Summary of eligibility criteria	
• Age between 50 and 85• In stable medical condition and willing and able to perform study procedures.• Fluent in written and verbal Dutch.• Capable of giving informed consent.
Maximum duration of treatment of a subject	/
Version and date of final protocol	v 1.2 27/10/2017
Version and date of protocol amendments	

2. Background, rationale and novelty

Alzheimer's disease (AD) is the most common neurodegenerative disorder and the leading cause of dementia worldwide.¹ A growing number of people are surviving into their 80s-90s and the number of AD patients projected to nearly triple in the next three decades, affecting 80-90 million people worldwide by 2040.^{1,2} As such, AD will become the third cause of death for older people, just behind cardiovascular disease and cancer. In contrast to the latter, AD cannot be prevented, slowed or cured. AD represents an enormous socio-economic burden and has become a trillion dollar disease.³ Despite decades of intensive research, diagnosis and treatment remain challenging for AD. A string of recent failures in clinical trials for AD drugs has pointed out that our understanding of the disease is still far from complete. More in detail, three major reasons underlying this treatment gap have been identified:

- i. **The lack of techniques for patient screening and early diagnosis.**
- ii. **The incomplete understanding of the complex interplay of pathological processes that underlie AD.**
- iii. **The many hurdles between drug discovery and approval.**

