The main contribution will consist of the examination of the validity of retinal biomarkers as a diagnostic measure for A β -positivity, and the determination of their ability to quantitatively measure change in A β load. At the end of the project, we aim to deliver a research setup of a hyperspectral camera for retinal imaging, standardized image acquisition protocols for retinal imaging of AD biomarkers using different technologies (including hyperspectral imaging) and a data science approach for AD diagnosis. Proof-of-concept for the predictive value of multimodal imaging of selected retinal biomarkers in diagnosing and classifying AD patients will be delivered.

This may be in the future useful for screening, early diagnosis and follow-up of AD. This is of major importance because AD has a long preclinical and prodromal phase, and by the time symptoms suggestive of a clinical diagnosis appear, neurodegeneration may have led to damage too extensive to repair.

The primary objective of the human clinical diagnostic trial is to validate the retinal biomarkers against A β load measured with ^{18}F -flutemetamol PET as standard-of-truth. The cross-sectional data collection is mainly aimed at exploring retinal biomarkers as a diagnostic measure for A β -positivity, while gathering the longitudinal information is mainly aimed at determining their ability to quantitatively measure change in A β load. The discriminative value of retinal imaging will be assessed (phase 1) and

subsequently evaluated (phase 2). All patients will be followed longitudinally over the course of 24 months.

This is an open-label longitudinal biomarker study without investigational medicinal product in subjects in different stages of the AD spectrum.

The data that we will collect consist of amyloid imaging, MRI, blood, genetic, general health and cognitive data, as well as visual acuity, ocular biomicroscopy and funduscopy, fundus photographs, hyperspectral retinal images, Optical Coherence Tomography (OCT) retinal images and OCT angiography (OCT-A) retinal images. Subjects will be followed longitudinally. In the current study we will primarily investigate the potential of non-invasive, multimodal retinal imaging for the early detection of Alzheimer's disease and for the evaluation of disease progression. This will be done in comparison with amyloid imaging and neuropsychological evaluations.

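### The accuracy endpoint is for multimodal retinal imaging, but the analyses fixed in sections 3.1 and 3.2 take one parameter at a time and do not by themselves yield it

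*Protocol*

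**What the plan says.** **What is promised.** The third item under Endpoints in the Protocol synopsis is "determination of diagnostic accuracy of multimodal retinal imaging", expressed as sensitivity and specificity. It applies only if technical capability has first been shown to be acceptable. Section 3 adds a deliverable: "Proof-of-concept for the predictive value of multimodal imaging of selected retinal biomarkers" in diagnosing and classifying patients. It also announces a data-science approach to diagnosis and names missing integrative software among the problems to be tackled.

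**What is fixed as analysis.** Section 3.1 runs ROC analyses of the individual measures, and then "The three ophthalmological parameters with the best diagnostic accuracy will be selected as primary outcome measures". Section 3.2 sets out a contingency table against amyloid PET in which "cognitively intact subjects will be classified according to one ophthalmological parameter". It continues: "This will be done for the three parameters that have been selected based on the phase 1 data". The same is planned for amyloid-negative intact subjects against amyloid-positive MCI patients. Section 8.2 only refers back to section 3.

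**What agrees with those analyses.** The secondary objective in the synopsis reads "To evaluate the diagnostic performance of selected ocular biomarkers for Alzheimer's disease", and the phase 2 objective in section 3.2 is likewise worded for three measures.

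**The concern.** The sensitivity and specificity of a multimodal test belong to a rule that turns several measurements into one positive or negative call. No such rule appears in the Protocol: there is no score, no joint model and no and/or criterion. Followed as written, the plan reports how each of three parameters performs alone.

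Two consequences follow.

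- Taking the three best parameters on AUC puts no constraint on where they come from. If all three are OCT thickness measures, phase 2 evaluates a single modality.
- If a combination is first devised after phase 2 results are known, its components, rule and cut-off can be chosen on those results. That would undo the independent validation for which phase 2 was designed.

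**Working it through.** **1. Count what the plan yields.** Parameters: 3 (section 3.1). Contrasts: 2 (section 3.2: amyloid-negative intact against amyloid-positive intact, and against amyloid-positive MCI). Single-parameter pairs: 3 × 2 = 6. Combined pairs: 0.

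**2. Reproduce the plan's own figure.** Section 8.1 gives at least 13 per group for alpha 0.05, power 0.90 and effect size 1.33. A two-sided two-sample t-test gives 12.92, hence 13, with power 0.902 at 13 and 0.984 at the planned 20 per group. The figure reproduces. It concerns a mean difference in one parameter, so 1.33 can serve as a standardised effect d for a single parameter.

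**3. One parameter at d = 1.33.** Assume normal distributions with equal variance.

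- AUC = Φ(d/√2) = Φ(0.940) = 0.83
- Sensitivity = specificity at the symmetric cut-off = Φ(d/2) = Φ(0.665) = 0.75

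**4. The six pairs do not determine a combined result.** Take three parameters at 0.747 each and assume independence.

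| Rule | Sensitivity | Specificity |
|---|---|---|
| One parameter | 0.75 | 0.75 |
| At least 2 of 3 positive: p³ + 3p²(1−p) | 0.84 | 0.84 |
| Any positive: 1−(1−p)³ and p³ | 0.98 | 0.42 |

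The answer depends on the rule, and also on the correlation between parameters. The Protocol gives neither.

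**5. Equal-weight composite, favourable case.** If all three parameters have d = 1.33 and common correlation ρ (an assumption, since the Protocol gives none), the mean of z-scores has D = 1.33 × √(3/(1+2ρ)).

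| ρ | D | AUC = Φ(D/√2) | Sens = spec = Φ(D/2) |
|---|---|---|---|
| 0.3 | 1.82 | 0.90 | 0.82 |
| 0.5 | 1.63 | 0.88 | 0.79 |
| 0.7 | 1.49 | 0.85 | 0.77 |

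**6. Equal-weight composite, unequal effects.** In general D = (d₁+d₂+d₃)/√(3(1+2ρ)). Assume effects of 1.33, 0.5 and 0.5.

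- ρ = 0.3: D = 2.33/√4.8 = 1.06, sens = spec = Φ(0.53) = 0.70
- ρ = 0.5: D = 2.33/√6 = 0.95, sens = spec = Φ(0.48) = 0.68

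Both are below the 0.75 of the best parameter alone. To break even, each of the other two needs d = 1.33 × (√(3(1+2ρ)) − 1)/2, which is 0.79, 0.96 or 1.12 at ρ = 0.3, 0.5 or 0.7.

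**7. Precision.** With 20 per group, an observed 15/20 = 0.75 has an exact 95% interval of 0.51 to 0.91 (Wilson 0.53 to 0.89).

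**The case against.** A reader might infer that the trial cannot report its endpoint. The documents do not support that. Section 3.1 has every participant undergo hyperspectral imaging, OCT, OCT angiography and fundus photography, and phase 2 uses the same procedures, so a combined classification can be computed. The sentence in section 3.2 describes the primary analysis and excludes no other.

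A reader might also infer that the plan throws away a sure gain in accuracy. That is not shown either. The value 1.33 is one effect size taken from one earlier OCT study, and nothing in the Protocol supports it for OCT angiography or hyperspectral measures. Step 6 shows that a composite can lose accuracy, and step 7 shows that even the favourable gain is small against the interval at 20 per group.

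Other parts of the opposing case also have force. The endpoint is conditional and is one of three. The secondary and phase 2 objectives fit a parameter-by-parameter analysis, so the synopsis may simply be loosely worded, with multimodal meaning that several modalities are acquired and the best parameters then validated singly. That is why rewording is an acceptable remedy. If one device proves best, keeping its parameters is a legitimate exploratory result.

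The detail of a composite could also sit in an analysis plan that is not shown, and its absence from the Protocol is not the complaint. The complaint is that the Protocol itself states the accuracy analyses, and those do not produce the quantity that it names as an endpoint. Announcing a data-science approach in section 3 does not supply a rule or say when it will be fixed.

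**Conclusion.** The point holds as an internal mismatch. The synopsis endpoint and the section 3 deliverable are for multimodal imaging, while the analyses stated in sections 3.1 and 3.2 give six single-parameter pairs and no combined estimate. Selection on AUC alone does not ensure that more than one modality reaches phase 2. This count rests on the text alone and needs no assumption about effect sizes.

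The effect on accuracy is illustrative. If all three parameters had d = 1.33, sensitivity = specificity would move from 0.75 to about 0.77–0.82 for ρ from 0.7 down to 0.3. With effects of 1.33, 0.5 and 0.5 it would fall to about 0.70 or 0.68 at ρ = 0.3 or 0.5. The reason to act is therefore to estimate the stated endpoint without data-driven choice. It is a worthwhile and cheap improvement, and the single-parameter analyses are not invalid without it.

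**What to change.** Keep the three single-parameter tables as primary. Add one secondary combined classification, with everything locked from phase 1 before phase 2 data are seen:

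- **Components:** parameters from at least two modalities, with a written rule for what enters if the three best all come from one.
- **Rule:** for example, the equal-weight mean of z-scores, standardised on the phase 1 amyloid-negative controls with signs fixed from phase 1. No weights should be fitted at 15 per group.
- **Cut-off:** set in phase 1 and applied unchanged in phase 2 to both contrasts.
- **Report:** sensitivity and specificity with confidence intervals, next to the single-parameter results.

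If the sponsor does not intend a combined test, reword the synopsis endpoint and the section 3 deliverable to the accuracy of each selected parameter.

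Either route needs wording only, with no extra participants or measurements. The composite adds one analysis per contrast, taking the count from 6 to 6 + 2 = 8, and the two additions belong in the multiplicity accounting.
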